6.2 IMPORTANT PROTOCOL DEVIATIONS

Data discrepancies and deviations from the CTP will be identified for all patients enrolled in this trial.

Consistency check listings (for identification of deviations of protocol-defined time windows) and a list of protocol deviations (e.g. deviations in drug administration, in blood sampling times, etc.) will be provided to be discussed at the trial oversight meetings, the report planning meetings and the report alignment meeting (TOMs/RPMs/RAM). At these meetings, it will be decided whether a discrepant data value can be used in analyses or whether it must be corrected in the clinical database. Each protocol deviation must be assessed to determine whether it is an important protocol deviation (iPD). For definition of iPDs, and for the process of identification of these, refer to the BI reference document "Identify and Manage Important Protocol Deviations (IPD)" ([2](#)).

If any iPDs are identified, they are to be summarised into categories and will be captured in the TOMs minutes and in the decision log. Categories which are considered to be iPDs in this trial are defined in the DV domain (excel Spreadsheet). If the data show other iPDs, the definition in the DV domain will be supplemented accordingly by the time of the TOMs/BRPMs/RAM.

Not all iPDs will lead to exclusion from analysis sets. iPDs leading to exclusion from analysis sets are indicated as such in the DV domain.

All iPIDs and all COVID-19 related PDs will be summarised and listed.

6.3 PATIENT SETS ANALYSED

The following analysis sets will be defined for this trial:

- **Enrolled set (ES)**
This patient set includes all patients of the Screening Cohort and of the Study Cohort who signed informed consent.
It will be used for analyses for disclosure of AE data.
- **Enrolled set – Screening Cohort (ES-Screen)**
This patient set includes all patients of the Screening Cohort who signed informed consent.
It will be used for analyses of patient disposition for the Screening Cohort.
- **Entered set (ENTS) – Screening Cohort**
The entered set includes all patients of the Screening Cohort who entered the trial (“Will the subject enter the study?” is ticked “Yes” on the Eligibility page of the eCRF).
- **Enrolled set– Study Cohort (ES-Study)**
This patient set includes all patients of the Study Cohort who signed informed consent. It will be used for analyses of patient disposition for the Study Cohort.
[In case a patient is re-screened, the last attempt will be considered.]
- **Randomised set (RS) – Study Cohort**
The randomised set includes all randomised patients, whether treated or not.
Since patients in the Screening Cohort will not be randomised, RS only contains patients of the Study Cohort.
It is expected that the RS and the FAS (see below) will not differ. Therefore, all analyses will be performed on the FAS.
- **Safety set (SAF) – Study Cohort**
The safety set includes all patients who were randomised and treated with any amount of study drug. The treatment assignment will be determined based on the actual treatment the patient received.
Since patients in the Screening Cohort will not be randomised, SAF only contains patients of the Study Cohort.
- **Full analysis set (FAS) – Study Cohort**
The full analysis set includes all patients of the Study Cohort who provided a baseline value and at least one post-baseline value for at least one secondary endpoint or further efficacy endpoint.
- **RNA sequencing set (RSS) – Study Cohort**
This patient set includes all patients in the safety set who provide a valid baseline and at least one valid post-baseline observation for at least one gene expression variable of

biopsy. This patient set will be used for analyses related to RNA sequencing. By definition of the safety set, RSS only contains patients of the Study Cohort.

Handling of Treatment Misallocations in Analysis Sets

If a patient is randomized but took incorrect treatment during the study, then the following will apply for safety reporting:

If a patient randomized to Placebo inadvertently is administered a dose of spesolimab during the first 12 weeks of the trial then that patient will be reported in the spesolimab treatment arm (treatment period 1 and 2) for all safety analyses. If a patient is randomized to spesolimab and was only administered placebo during the first 12 weeks of the trial then that patient will be reported in the placebo treatment arm (treatment period 1). If a patient is randomized to spesolimab and was only administered placebo during the entire trial (that is, within both first and last 12 weeks) then that patient will be reported in the placebo treatment arm (treatment period 1 and 2).

Primary endpoint analysis:

If a patient is randomized to placebo/spesolimab but received spesolimab /placebo on Day 1 then that patient will be reported in the spesolimab/placebo treatment arm, respectively. Note that study drug the patient was not randomized to was administered at Week 4 or later does not affect the primary endpoint analysis since biopsies are scheduled pre-dose at Week 4.

Table 6.3: 1 Patient sets analysed

Class of endpoint	Patient set					
	ES	ENTS	ES-Screen/ ES-Study	SAF	FAS	RSS
Disposition	OR ²	OR ¹	OR		OR	
Exposure and compliance				OR		
iPD		OR ¹			OR	
Demographic/baseline endpoints		OR ¹			OR	
Primary endpoint and further endpoints related to gene expression data						OR
Secondary efficacy endpoints					NRI OC-IR ^S	
[REDACTED]					[REDACTED]	
Safety endpoints				OR OC- IR		
Use of rescue medication					OR	
[REDACTED]						
[REDACTED]						

¹ The patient set will be used for analysis of the Screening Cohort data.

² The patient set will be used for analysis combined data of the Screening Cohort and the Study Cohort.

^S sensitivity analysis

NRI = no response imputation, OR = original results, OC = observed case, OC-IR = observed cases including rescue
 For explanation of the different approaches with regard to missing data see [Section 6.6](#).

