### 7.3 PLANNED ANALYSES

All individual data will be listed.

The statistical analysis of the Screening Cohort will be based on the following analysis sets:

- Enrolled set (ES – Screening Cohort)  
This patient set includes all patients of the Screening Cohort who signed informed consent.  
It will be used for analyses of patient disposition.
- Entered set (ENTS – Screening Cohort)  
The entered set includes all patients of the Study Cohort who entered the trial.

The statistical analysis of the Study Cohort will be based on the following analysis sets:

- Enrolled set (ES – Study Cohort)  
This patient set includes all patients of the Study Cohort who signed informed consent.  
It will be used for analyses of patient disposition.
- Randomised set (RS): The randomised set includes all randomised patients, whether treated or not.  
Since patients in the Screening Cohort will not be randomised, RS only contains patients of the Study Cohort.
- Safety set (SAF): The safety set includes all patients who were randomised and treated with any amount of study drug. The treatment assignment will be determined based on the actual treatment the patient received.  
Since patients in the Screening Cohort will not be randomised, SAF only contains patients of the Study Cohort.
- Full analysis set (FAS)  
The full analysis set includes all patients of the Study Cohort who provided a baseline value and at least one post-baseline value for at least one secondary endpoint or

further efficacy endpoint. Following the intent-to-treat principle, patients will be analysed according to the treatment they were assigned to at randomisation.

- RNA sequencing set (RSS): This patient set includes all patients in the safety set who provide a valid baseline and at least one valid post-baseline observation for at least one gene expression variable of biopsy. This patient set will be used for analyses related to RNA sequencing.

By definition of the safety set, RSS only contains patients of the Study Cohort.

In the TSAP, the FAS definition may be updated, and further analysis data sets may be defined.

The following analyses of this trial protocol, in chronological order, are planned:

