6.6 HANDLING OF MISSING DATA AND OUTLIERS

Section 7.5 of the CTP describes the handling of missing data.

Based on the different reasons for patients' data missing, different approaches will be used to assess the impact of missing data on the endpoints of this trial, depending upon the type of the endpoint. The following approaches are applied in this trial:

- The original results (OR) approach implies the presentation of data exactly as observed (not using time windows as described in [Section 6.7](#) and not setting values to missing). OR analysis will be performed on parameters and endpoints for which it is not meaningful to apply any imputation rule for the replacement of missing values.
- Observed cases (OC) approach will include all collected data, without imputation for any missing data but all values measured after any use of rescue medication will be excluded from the analysis. Note that patients that took rescue treatment are not kept in the denominator for categorical endpoints at subsequent time points.
- Observed cases including rescue (OC-IR) approach is an extension of the OC approach which includes additionally all values which were measured after rescue medication intake.
- The no response imputation (NRI) approach is applied for binary endpoints. Missing values will be imputed described in the following:
 1. If a patient takes a rescue medication (as defined in [Section 5.4.3](#)) for the treatment of disease under study or died due to any cause, then all data subsequent to the intake of such rescue will be considered to be missing.
 2. For endpoints which are measured at multiple visits, if there are data at visits both before and after the visit with a missing outcome, then impute as success only if both neighbouring visits also represent a success (independent of whether the preceding and following observations were selected for analysis based on time windows described in [Section 6.7](#)), and there is no intervening rescue treatment use. For all patients with a missing visit outcome, impute as a failure to achieve a response.

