7.5.2 Secondary endpoints

The analysis of secondary endpoints will be based on the FAS using NRI approach and will be done by “planned treatment”.

Perianal fistula response, perianal fistula remission, and combined perianal fistula remission will be derived based on reported fistula characteristic data as described in [Section 5.2.2](#) for Week 12, and Week 24;

The proportion of patients at Week 12 will be summarized descriptively presenting patient frequencies and proportions together with 95% exact unconditional confidence intervals based on the score statistic for the risk difference spesolimab minus Placebo (if feasible) (cf. [Additional Section 9.2.](#))

[figure not shown]
[Redacted]

[Redacted]

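### The secondary endpoints use non-response imputation inside a FAS that needs a post-baseline efficacy value, so a randomised patient without one is dropped, not counted as a failure

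*SAP*

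**What the plan says.** - **Analysis set and missing-data rule.** SAP 7.5.2: "The analysis of secondary endpoints will be based on the FAS using NRI approach", by planned treatment. Table 6.3:1 agrees. It adds one sensitivity analysis, observed cases including rescue (OC-IR), also under the FAS.
- **Entry to the FAS.** SAP 6.3 admits Study Cohort patients who "provided a baseline value and at least one post-baseline value for at least one secondary endpoint". The sentence then widens the choice of endpoint, so the post-baseline part in full is "at least one post-baseline value for at least one secondary endpoint or further efficacy endpoint". Protocol 7.3 sets the same condition.
- **Randomised set (RS).** SAP 6.3: "The randomised set includes all randomised patients, whether treated or not". It has no column in Table 6.3:1. The reason given is: "It is expected that the RS and the FAS (see below) will not differ. Therefore, all analyses will be performed on the FAS".
- **NRI.** SAP 6.6 allows a missing visit to be imputed as a success only when both neighbouring visits are successes with no rescue in between. Otherwise: "For all patients with a missing visit outcome, impute as a failure to achieve a response".
- **Denominator.** SAP Section 7 bases percentages on every patient in the set concerned, with or without a value.
- **Intention to treat.** Protocol 7.3, in the FAS definition: "Following the intent-to-treat principle, patients will be analysed according to the treatment they were assigned to at randomisation".

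**The concern.** NRI needs no post-baseline value: a patient with no observed outcome is a failure by rule. The FAS does need one, and it is applied first. The patients it removes are those with nothing observed after baseline, and NRI would have counted every one of them as a failure. Whether a patient has such a value is known only after randomisation and may be related to treatment.

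What is at stake is the responder proportion in each arm and the risk difference with its interval. With about 10 patients per arm, one patient in or out of a denominator is visible in the estimate. If one arm loses more such patients, its response rate rises for a reason that has nothing to do with healing.

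**Working it through.** **Step 1. Who is dropped and who is kept.** Setting SAP 6.3, 6.6 and 6.7 side by side:

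| Randomised patient | In FAS? | Counted at Week 12 as |
|---|---|---|
| Never treated (SAP 6.7 defines baseline by start of trial treatment, so nothing is post-baseline) | No | Not counted |
| Treated, lost before any post-baseline efficacy value | No | Not counted |
| Treated, has an early efficacy value, lost before Week 12 | Yes | Failure by NRI |
| Takes rescue after an early efficacy value | Yes | Later data set to missing, then failure |

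Only the first two rows are affected.

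**Step 2. Is there a fallback?** No. The statement that RS and FAS will match is an expectation. The SAP's own disposition table has a line for patients randomised but not treated, and Section 7 allows an important protocol deviation to exclude a patient from the FAS, so the SAP itself allows for a difference. OC-IR starts from the FAS and cannot bring anyone back.

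**Step 3. Size.** The plan has no figure to reproduce: Protocol 7.7 bases the sample size on feasibility, with no response or dropout rate.

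Inputs from the documents: about 20 patients, 1:1 (Protocol 3.1), so n = 10 per arm; exact unconditional 95% interval based on the score statistic, spesolimab minus placebo (SAP 7.5.2). Assumed: responders x₁ = 4 (spesolimab) and x₂ = 1 (placebo); k₁ and k₂ patients per arm with no post-baseline efficacy value.

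- All randomised, missing = failure: RD = x₁/10 − x₂/10
- FAS as written: RD = x₁/(10 − k₁) − x₂/(10 − k₂)
- Shift, FAS minus all randomised: x₁k₁/[10(10 − k₁)] − x₂k₂/[10(10 − k₂)]

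Example, k₁ = 2 and k₂ = 0: shift = (4 × 2)/(10 × 8) = 0.10.

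The intervals invert two one-sided 2.5% tests of the score statistic, maximised over the nuisance proportion, on a grid. Limits are good to about 0.01.

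| Dropped from FAS | Proportions | RD | 95% CI (about) | Shift |
|---|---|---|---|---|
| Nobody (same as all randomised) | 4/10 vs 1/10 | 0.30 | −0.10 to 0.65 | 0 |
| 1 spesolimab | 4/9 vs 1/10 | 0.34 | −0.07 to 0.70 | +0.04 |
| 2 spesolimab | 4/8 vs 1/10 | 0.40 | −0.05 to 0.76 | +0.10 |
| 1 placebo | 4/10 vs 1/9 | 0.29 | −0.14 to 0.65 | −0.01 |
| 2 placebo | 4/10 vs 1/8 | 0.275 | −0.19 to 0.66 | −0.025 |
| 1 per arm | 4/9 vs 1/9 | 0.33 | −0.10 to 0.70 | +0.03 |

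**Step 4. Other assumed counts.** With 3 and 1 responders and up to two patients dropped, the shift runs from −(1 × 2)/80 = −0.025 to (3 × 2)/80 = +0.075. With 5 and 2 responders it runs from −(2 × 2)/80 = −0.05 to (5 × 2)/80 = +0.125.

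**The case against.** The case against has real weight.

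- **The affected group is small.** Any post-baseline value on any efficacy endpoint keeps a patient in. SAP Section 3 names CDAI, PDAI, SES-CD, IBDQ, CRP and faecal calprotectin among the further endpoints. The first analysis window in Table 6.7:1 opens on Day 2, and unscheduled measurements count. Randomisation and first dose are both planned for Visit 2, so untreated patients should be rare. This stands.
- **Stopping drug is not leaving the trial.** Protocol 6.2.2.4 encourages patients who stop treatment to keep attending to Week 24. A patient who stops after an infusion reaction is dropped only if no later efficacy value exists. This stands.
- **Exclusions would be visible.** Disposition is shown by randomised treatment, the size of each analysis set is reported and individual data are listed. A reader could rebuild the all-randomised proportion. That helps, but it does not correct the planned estimate.
- **Nothing confirmatory depends on it.** Protocol 7.2 plans no confirmatory test. In the illustration every interval includes zero and they overlap heavily. This stands.

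Two stronger readings are tempting. A reader might infer that everyone without a Week 12 outcome is removed; the table in Step 1 shows that later dropouts stay in as failures. A reader might also infer that the SAP breaks a protocol commitment to intention to treat. The Protocol 7.3 sentence spells out only analysis by assigned arm, and it sits in the same definition as the post-baseline condition. The SAP keeps to it by analysing by planned treatment.

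**Conclusion.** The point holds in a limited form. NRI works only inside a set that has already excluded randomised patients with no post-baseline efficacy value, and the only protection is an expectation that there will be none. If that expectation is met, the effect is exactly zero. If not, under the assumed 4 and 1 responders with up to two patients dropped, the risk difference moves by between −2.5 and +10 percentage points. Over all the responder counts tried, the range is −5 to +12.5 points. The direction depends on which arm loses patients, so a bias in favour of spesolimab cannot be presumed. All responder and dropout counts are assumptions. The consequence is for descriptive estimates in an exploratory trial. The reason to act is that the remedy costs almost nothing: if the sets coincide the results are identical, and if they differ the randomised set avoids selection after randomisation.

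**What to change.** In SAP 6.3, 7.5.2 and Table 6.3:1, analyse the three secondary endpoints on the randomised set, by randomised arm, with NRI (missing counted as failure). Add an RS column to the table. Delete the sentence that moves all analyses to the FAS because the two sets are expected to match. Keep the FAS for endpoints that need both a baseline and a post-baseline value.

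The cost is wording only: the RS is already defined and no new data are needed. Protocol 7.3.2 names the FAS for efficacy endpoints, so the change should be recorded in SAP Section 4. The downside is that response rates may be slightly less favourable if the sets differ, because untreated patients and those lost very early would then count as failures.

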6.5 POOLING OF CENTRES

It is planned that up to 8 patients will be entered into the Screening Cohort and approximately 20 patients will be entered into the Study Cohort. The trial will be conducted in multiple centres across several countries and a small number of patients entered per centre can be expected. Given the low number of patients per centre, separate analyses by centre are not meaningful and not desirable. All patients from all centres will be pooled for statistical analysis.

6.6 HANDLING OF MISSING DATA AND OUTLIERS

Section 7.5 of the CTP describes the handling of missing data.

Based on the different reasons for patients' data missing, different approaches will be used to assess the impact of missing data on the endpoints of this trial, depending upon the type of the endpoint. The following approaches are applied in this trial:

- The original results (OR) approach implies the presentation of data exactly as observed (not using time windows as described in [Section 6.7](#) and not setting values to missing). OR analysis will be performed on parameters and endpoints for which it is not meaningful to apply any imputation rule for the replacement of missing values.
- Observed cases (OC) approach will include all collected data, without imputation for any missing data but all values measured after any use of rescue medication will be excluded from the analysis. Note that patients that took rescue treatment are not kept in the denominator for categorical endpoints at subsequent time points.
- Observed cases including rescue (OC-IR) approach is an extension of the OC approach which includes additionally all values which were measured after rescue medication intake.
- The no response imputation (NRI) approach is applied for binary endpoints. Missing values will be imputed described in the following:
 1. If a patient takes a rescue medication (as defined in [Section 5.4.3](#)) for the treatment of disease under study or died due to any cause, then all data subsequent to the intake of such rescue will be considered to be missing.
 2. For endpoints which are measured at multiple visits, if there are data at visits both before and after the visit with a missing outcome, then impute as success only if both neighbouring visits also represent a success (independent of whether the preceding and following observations were selected for analysis based on time windows described in [Section 6.7](#)), and there is no intervening rescue treatment use. For all patients with a missing visit outcome, impute as a failure to achieve a response.
- Imputation technique last observation carried forward (LOCF): The LOCF approach will be used as the imputation strategy to replace missing values either at intermediate visits or due to early withdrawal from the trial. The last available value, excluding baseline, will be carried forward to all subsequent visits within the on-treatment period at which a measurement is missing. Values measured after the day of first rescue medication intake (as defined in [Section 5.4.3](#)) will be set to missing and the missing values within the on-treatment period will be imputed by LOCF.

The following sections describe which imputation approach is used for the different endpoints.

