Assignment of efficacy observations to visits based on time windows will be based on the non-imputed (observed) data after setting values after rescue medication intake to missing (if applicable, i.e. for the “LOCF” and “NRI” approaches and the “OC” approach defined in [Section 6.6](#)). Visits which were not assigned a value based on time windows will thereafter

be imputed for the NRI approaches defined in [Section 6.6](#). Imputation of efficacy endpoints (binary as well as continuous) will be performed based on all available observations, irrespective of whether the observation was selected in any time window.

For derivation of the last value during the on-treatment period, the minimum value during the on-treatment period, and the maximum value during the on-treatment period, all values during the on-treatment period (including unscheduled and repeated measurements) will be considered; these will be derived for analysis of laboratory and vital signs data. For identification of potentially clinically significant abnormal laboratory values, all values (including unscheduled and repeated measurements) will be considered.

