Furthermore, the use of rescue therapy including rescue medication (eCRF) and rescue non-drug surgical therapy (cf. [Section 5.4.3](#)) will be summarised with frequency and percentage of patients together in one table by category. Summaries will be presented for rescue therapies during treatment period 1 and during treatment period 2 (similar as for concomitant medication)..

Concomitant use of non-drug therapies will be summarised with frequency and percentage of patients by SOC and preferred name. Summaries will be presented for prior non-drug therapies, concomitant non-drug therapies during treatment period 1 and during treatment period 2 (similar as for concomitant medication) for the Study Cohort. For the Screening Cohort, the summaries will be presented over the whole study duration.

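### On the visible SAP wording, the NRI rule discards data after rescue medication or death but not after rescue or barred fistula surgery, so some operated patients can be scored as Week 12 response or remission

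*SAP*

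**What the plan says.** **Rule that discards data.** NRI rule 1 in SAP 6.6 has two triggers, rescue medication as defined in SAP 5.4.3 and death from any cause; "then all data subsequent to the intake of such rescue will be considered to be missing". The visit-assignment step in SAP 6.7 works on observed data "after setting values after rescue medication intake to missing". The LOCF rule in 6.6 uses the same trigger: "Values measured after the day of first rescue medication intake". OC-IR, the sensitivity approach for the secondary endpoints, is the one "which includes additionally all values which were measured after rescue medication intake".

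**Where surgery appears.** SAP 7.2 summarises "the use of rescue therapy including rescue medication (eCRF) and rescue non-drug surgical therapy", citing the same Section 5.4.3. It adds: "Summaries will be presented for rescue therapies during treatment period 1 and during treatment period 2".

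**Looser terms.** NRI rule 2 imputes success for a missing visit only if both neighbouring visits are successes "and there is no intervening rescue treatment use". SAP Table 6.3:1 has a single row, "Use of rescue medication", although 7.2 puts medication and surgery in one table.

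**Protocol.** Table 3.1:1 defines rescue medication, and Section 4.2.1 defines rescue treatment, in terms of medication only. Section 4.2.2.2 bars fistula surgery other than seton drainage, requires discontinuation if it happens, and gives interference with the clinical endpoints as the reason.

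**Endpoint derivation.** SAP 5.2.2 counts closed and open fistulas among those draining at baseline. It notes that surgery after Visit 1c lowered the number of draining fistulas in a few patients, and that the post-baseline form refers to those left after surgery. It does not date that surgery against first dose.

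**The concern.** NRI is meant to stop a patient who needed something beyond study drug from counting as a treatment success. For medication the rule does that. For surgery, which closes or removes a fistula directly, the visible wording does not: an operation is not an intake, and the SAP names surgery separately where it means surgery.

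SAP 7.5.2 applies NRI on the FAS to perianal fistula response, remission and combined remission, so all three could credit an arm with a surgical result. That is the interference the protocol gives as its reason for the bar. OC-IR cannot expose the problem, because it keeps values after rescue by design.

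**Working it through.** The plan attaches no figure to this rule, so there is none to reproduce. Three checks follow.

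**1. Does the Week 12 value survive?** A patient taken off drug stays in the trial (protocol 3.3.4.1) and is encouraged to attend to Week 24 (protocol 6.2.2.4). Visit data count while within the residual effect period of 112 days after the last dose (SAP Tables 6.1:1 and 6.7:1). Week 12 is Day 85, or Day 89 at the end of the protocol window.

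- Last dose Day 1: 1 + 112 = Day 113
- Last dose Day 29: 29 + 112 = Day 141
- Last dose Day 57: 57 + 112 = Day 169

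All are later than Day 89, so stopping drug does not remove the value.

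**2. How is it scored?** With o closed openings, ρ open openings and ε new fistulas, SAP 5.2.2 gives response if o/(o+ρ) ≥ 0.5 and ε = 0, and remission if o/(o+ρ) = 1 and ε = 0. The formulas have no surgery term. The operated opening could be counted as closed, or dropped if the after-surgery note also covers surgery after first dose. The last column counts it as not closed, which assumes that it would not have closed without the operation. ε = 0 throughout.

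| Openings: operated / closed without surgery / open | Operated counted closed | Operated dropped | Surgery not credited |
|---|---|---|---|
| 2: 1 / 0 / 1 | 1/2 response | 0/1 non-response | 0/2 non-response |
| 2: 1 / 1 / 0 | 2/2 remission | 1/1 remission | 1/2 response only |
| 2: 2 / 0 / 0 | 2/2 remission | 0/0 undefined | 0/2 non-response |
| 3: 1 / 1 / 1 | 2/3 response | 1/2 response | 1/3 non-response |

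In the second and fourth rows surgery gains a success under either reading. In the first and third it does so only if the operated opening is counted closed. Combined remission also needs no collection above 2 cm on MRI.

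**3. What is one patient worth?** The protocol synopsis gives about 10 patients per arm, so one patient is 1/10 = 10 percentage points. The responder counts below are assumed, since the documents give none. Intervals follow the method named in SAP 7.5.2 (exact unconditional, score statistic), found by inverting two one-sided tests at 0.025 and maximising over the nuisance proportion.

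| Operated patient | Handling | Spesolimab vs placebo | Difference (95% CI) |
|---|---|---|---|
| Spesolimab | scored success | 4/10 vs 1/10 | 0.30 (−0.11 to 0.66) |
| Spesolimab | excluded from FAS | 3/9 vs 1/10 | 0.23 (−0.17 to 0.61) |
| Spesolimab | scored non-response | 3/10 vs 1/10 | 0.20 (−0.19 to 0.57) |
| Placebo | scored success | 3/10 vs 2/10 | 0.10 (−0.31 to 0.49) |
| Placebo | scored non-response | 3/10 vs 1/10 | 0.20 (−0.19 to 0.57) |

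Correcting an operated spesolimab responder shrinks the difference by 0.10. Correcting an operated placebo responder widens it by 0.10.

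**The case against.** **Surgery may already be covered.** Rule 1 takes its definition from SAP 5.4.3, the section that 7.2 also cites for surgical rescue. The mixed terms in rule 2 and Table 6.3:1 suggest that an umbrella meaning may be intended. Section 5.4.3 is not in the text available to us, and parts of 6.6.2, on efficacy endpoints, are redacted. This stands: the documents do not show that the plan omits surgery. They show that the visible wording does not include it. Rule 2 does not close the gap, because it acts only on outcomes already missing.

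**Surgery alone may earn nothing.** If the after-surgery note in SAP 5.2.2 covers operations after first dose, operated openings leave the count. A fully operated patient then gives 0/0, which NRI would plausibly treat as missing and normally as failure. This also stands in part. A reader might infer that barred surgery is automatically scored as success; that is not supported. But the second and fourth rows of the scoring table are successes even on this reading.

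**The deviation route.** An important protocol deviation could remove the patient from the FAS (SAP 6.2 and 7); the list of such deviations was not supplied. That would drop a failure rather than score it.

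**Low stakes.** The endpoints are descriptive, the primary endpoint is Week 4 gene expression, and 7.2 already tabulates rescue surgery by period, so a reader of about 20 patients would see it. This limits the severity but does not settle how those patients are scored.

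**Conclusion.** The point holds in conditional form. Unless SAP 5.4.3 or the redacted text in 6.6.2 already counts surgery, a patient with rescue or barred fistula surgery between first dose and Week 12 can keep an observed value, and some such patients would be scored as response or remission because of the operation. Each one moves the arm's rate by 10 points at 10 per arm. A new fistula, a collection above 2 cm (for combined remission) or a missing outcome can still make the patient a failure.

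Two further inferences are not supported. The first is that the rule favours spesolimab: the direction depends on which arm the operated patient is in. The second is that surgery after first dose has occurred: the few cases in SAP 5.2.2 are placed after Visit 1c, which is three weeks before first dose, and may all precede dosing. Whether an interval crosses zero in the illustration depends on the assumed counts and decides nothing, since protocol 7.2 plans no confirmatory test.

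Severity is minor to should-fix: it affects interpretation only and is cheap to repair.

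**What to change.** **SAP 6.6 (NRI rule 1, with OC and LOCF aligned) and 6.7.** Replace the rescue-medication trigger with *rescue therapy: rescue medication, or rescue non-drug surgical therapy per 5.4.3, or any fistula procedure restricted under protocol 4.2.2.2, excluding the protocol seton procedures, on or after Day 1*. Naming protocol 4.2.2.2 matters because nothing visible shows that the 5.4.3 surgical category includes every barred procedure. Under NRI, score non-response from that date and keep the patient in the FAS. If 5.4.3 already counts surgery, this edit mainly aligns the wording.

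**SAP 5.2.2.** State that the after-surgery reset applies only to surgery before first dose, and date the cases mentioned there against Day 1. For analyses that keep values after rescue (OC-IR), state that an opening operated on after first dose stays in the denominator and is not counted as closed. Post-dose surgery then cannot produce 0/0, and no separate rule for it is needed.

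**Cost.** SAP wording and a small programming change. SAP 7.2 already plans rescue summaries by treatment period, surgery included, which implies that surgery dates are held; confirm this. Response rates under NRI can only stay the same or fall. The LOCF edit is for consistency only, since the secondary endpoints use NRI.
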